#### 6.8 INTERIM ANALYSIS

Refer to Section 13.5 for details of the interim analysis.

#### 6.9 STUDY COMMITTEES

Sponsor representatives and Investigators who have enrolled at least 1 patient will review clinical data approximately every 2 weeks during the course of the Phase 1 part, at the end of Stage 1 and 2 of each tumor cohort, and ad hoc as required.

An independent Data Monitoring Committee (DMC) will periodically evaluate ongoing safety data at intervals planned to be no longer than 3 months (starting from the first data review meeting) and make appropriate recommendations regarding the conduct of Phase 2 of this study.

# 7 SELECTION OF PATIENTS

#### 7.1 NUMBER OF PATIENTS

Refer to Section 13.1.

#### 7.2 INCLUSION CRITERIA

- I 01. Signed written informed consent.
- I 02.  $\geq$ 18 years of age.
- I 03. Disease location amenable to mandatory tumor biopsy at baseline (unless clinically unfeasible\* as per the Investigator and after obtaining written agreement from sponsor representative, only for NSCLC cohort), and possibly at Cycle 2 Day 1. Fine needle aspirates are not acceptable. Availability of a tissue specimen from core needle or excisional biopsies, or resected tissue are required. Provision of archival tumor tissue sample obtained at the time of or after progression of immediate previous line of anticancer treatment is allowed to replace mandatory baseline biopsy. \*Clinically unfeasible: With a written opinion from the investigator that performing a biopsy will put the wellbeing of the subject at an excessive risk due to the location of the lesion.
- I 04. Based on the Investigator's judgment, at this time, chemotherapy is not the best treatment option for this specific patient. The eligibility of patient to take part in the study will be validated at the multidisciplinary collegial meeting in countries listed in Appendix I.

#### For mCRPC patients (I05 to I11):

- I 05. Histologically confirmed adenocarcinoma of the prostate (excluding neuroendocrine differentiation and/or small cell features).
- I 06. Metastatic disease documented by bone lesion on bone scan, or by measurable soft tissue disease by computed tomography (CT) or magnetic resonance imaging (MRI). Patients whose disease spread is limited to regional pelvic lymph nodes are not eligible.
- I 07. Surgically or medically castrated, with testosterone levels of <50 ng/dL (<2.0 nM). Patients who have not had a bilateral orchiectomy must have started androgen deprivation therapy with gonadotropin-releasing hormone (GnRH) analogue ≥4 weeks prior to initiation of IMP and continue such therapy throughout the study.
- I 08. At least 1 but no more than 2 previous androgen receptor-targeted agents (abiraterone and enzalutamide).

- I 09. Received up to 2 previous taxane-based chemotherapy regimens as per local standard of care (for example, docetaxel followed by cabazitaxel), unless per investigator's judgement a chemotherapy regimen is not appropriate for the specific patient. If the same taxane-based chemotherapy is used more than once, this will be considered as 1 regimen.
- I 10. No previous radium 223.
- I 11. Documentation of PD as assessed by the Investigator with at least 1 of the following within 6 months prior to first dose of IMP per Prostate Cancer Clinical Trials Working Group 3 (PCWG3) criteria (Appendix A) during or following the direct prior line of therapy.
  - Prostate-specific antigen progression defined by a minimum of 2 rising PSA levels with an interval of ≥1 week between each determination. The PSA value at the Screening visit should be ≥1 μg/L (1 ng/mL) if confirmed rise is the only indication of progression. Patients on systemic glucocorticoids for control of symptoms must have documented PSA progression while on systemic glucocorticoids before initiation of IMP.
  - Radiographic progression of soft tissue disease by RECIST 1.1 per PCWG recommendation (Appendix B). Previously normal (<1.0 cm) lymph nodes must have grown by ≥5 mm in the short axis from baseline or nadir and be ≥1.0 cm in the short axis to be considered to have progressed. If the node progresses to ≥1.5 cm in the short axis, it is measurable; nodes that have progressed to 1.0 cm to <1.5 cm are pathologic, subject to clinical discretion, and are nonmeasurable. For existing pathologic adenopathy and other soft tissue disease, progression is defined per RECIST 1.1.
  - Progression of bone metastasis is defined as 2 or more documented new bone lesions on a bone scan. Confirmation of ambiguous results by other imaging modalities (eg, CT or MRI) is obligatory if metastatic disease to bone is only defined by bone scan.

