## Laboratory assessments

- Serum pregnancy test: WOCBP must have a negative **serum** pregnancy test result within 7 days prior to the first dose IMP administration (local laboratory).
- Blood chemistry: includes AST, ALT, bilirubin (total and direct), alkaline phosphatase (ALP), LDH, sodium, potassium, chloride, bicarbonate/carbon dioxide, calcium, magnesium, phosphate, uric acid, urea or blood urea nitrogen (BUN), serum creatinine, eGFR (MDRD formula; Appendix H), glucose (fasting), albumin, total protein, thyroid stimulating hormone (TSH), and free T4 if TSH is outside of the normal range (local laboratory).
- Hematology: includes hemoglobin, hematocrit, red blood cell (RBC) count, white blood cell (WBC) count with differential, and platelet counts. If Grade 4 neutropenia, assess ANC every 2 to 3 days until ANC  $\geq$ 0.5 × 10^9/L and at least weekly thereafter until ANC  $\geq$ 1.0 × 10^9/L (local laboratory).
- Coagulation: includes prothrombin time or international normalized ratio (INR) and activated partial thromboplastin time (PTT) (local laboratory).
- Testosterone level (local laboratory).
- Blood typing interference test (local laboratory).
- Quantitative or semi-quantitative urinalysis: includes RBC, protein, glucose, pH, ketones, bilirubin, leucocytes, nitrates and specific gravity (local laboratory).

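### Inclusion criterion I07 gives one testosterone limit in two units that do not match: 50 ng/dL is 1.73 nM, and 2.0 nM is 57.7 ng/dL

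*Protocol*

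**What the plan says.** I07 admits an mCRPC patient who is "Surgically or medically castrated, with testosterone levels of <50 ng/dL (<2.0 nM"). The sentence is identical in the Clinical Trial Summary and in Section 7.2, so neither place corrects the other. The SAP does not restate the limit.

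Section 12.2 lists the baseline test as "Testosterone level (local laboratory"). The flowcharts in Sections 1.3 and 1.4 mark it at screening only. The trial plans about 15 sites worldwide. I found no conversion factor, no rounding convention and no statement of which unit governs in either document.

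Eligibility feeds into later steps of the plan:

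- **Response evaluable population.** Protocol Section 13.3.7 and SAP Section 2.3.7 restrict it to treated patients who meet every eligibility criterion. Protocol Section 13.4.4.1 repeats the response rate (RR) in it as a secondary analysis, and SAP Section 2.4.5 applies it to the efficacy analyses.
- **Protocol deviations.** Protocol Section 13.2.2 has major deviations settled before database lock, and SAP Section 2.2 summarizes them by cohort.
- **Cross-over from Cohort A-2.** Protocol Sections 6.4 and 12.2 require eligibility to be met again, apart from E03 and E08, with most screening procedures repeated.

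**The concern.** A reader takes a limit followed by a second unit in parentheses as one threshold. Other dual-unit limits in the same lists behave that way, for example PSA in I11 and haemoglobin in E20. If the two testosterone figures differ, I07 sets two thresholds, and the one applied depends on how a result is reported or read.

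At stake is consistent classification. Two men with the same testosterone could be treated differently at entry. A later eligibility check on the same man could also give different answers according to the unit used by the person checking. That would leave his deviation status and his membership of the response evaluable population undefined, and the question arises again at cross-over screening.

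**Working it through.** **Inputs**

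- Mass limit, 50 ng/dL: Protocol I07.
- Molar limit, 2.0 nM: Protocol I07.
- Molar mass of testosterone: not in the documents. It is taken as a chemical constant from the formula C19H28O2 and standard atomic weights: 19 × 12.011 + 28 × 1.008 + 2 × 15.999 = 288.431 g/mol. The result is checked over 288.0 to 289.0.

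**1. Try to reproduce the plan's figure.** The conversion is nM = (ng/dL × 10) / molar mass. For 50 ng/dL this is 500 / 288.431 = 1.73 nM. The printed 2.0 nM is not reproduced; it would need a molar mass of 500 / 2.0 = 250 g/mol.

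**2. Convert the other way.** 2.0 × 288.431 / 10 = 57.7 ng/dL.

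**3. Size of the gap.** 57.69 / 50 = 1.154, so the molar limit is 15.4% higher, or 57.7 − 50 = 7.7 ng/dL.

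| Molar mass (g/mol) | 50 ng/dL in nM | 2.0 nM in ng/dL | Excess |
|---|---|---|---|
| 288.0 | 1.736 | 57.6 | 15.2% |
| 288.431 | 1.734 | 57.7 | 15.4% |
| 289.0 | 1.730 | 57.8 | 15.6% |

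**4. Can rounding explain it?** To one decimal, 1.73 becomes 1.7. Only rounding to a whole number gives 2, and the protocol prints 2.0. Whole-number rounding may be how the figure arose, but the printed value still acts as a different limit.

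**5. Results that pass one limit and fail the other.** To two decimals these run from 1.74 nM (1.74 × 28.8431 = 50.2 ng/dL) to 1.99 nM (1.99 × 28.8431 = 57.4 ng/dL). Each is below 2.0 nM and not below 50 ng/dL.

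**6. Comparison with neighbouring criteria.** In I11, 1 μg/L and 1 ng/mL are exactly equal. In E20, haemoglobin 9 g/dL is 90 / 16.114 = 5.59 mmol/L on the usual monomer mass (an outside constant), printed correctly as 5.6. The testosterone pair does not follow that standard.

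**The case against.** The strongest reply is that the error has almost no consequence. Most of that reply stands.

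- **The band is narrow and the count is unknown.** The documents give no testosterone distribution and do not say that any site reports in nM. Any count of affected men rests on assumptions.
- **The primary analysis does not depend on it.** The all-treated population (Protocol Section 13.3.1, SAP Section 2.3.1) keeps every treated patient, whichever unit was applied at entry. The sample size is also unaffected.

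A reader might infer more than this from the mismatch. The documents do not support these stronger readings:

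- **That the testosterone value is the only safeguard of castration-resistant disease.** It is the only biochemical check. I07 separately requires surgical or medical castration, with a GnRH analogue begun at least 4 weeks before study treatment and continued unless the man has had an orchiectomy. I08 requires a prior androgen receptor-targeted agent, and I11 requires documented progression.
- **That men in the band would show PSA responses from deepening androgen suppression.** Confirmed PSA decline is one of two alternative routes to response in mCRPC, so the question is natural. Nothing in the documents shows such an effect in men already castrated and progressing. The PSA baseline is Cycle 1 Day 1 (Appendix A, Table 9), and starting other hormonal therapy is prohibited (Section 8.9.1).
- **That a misclassified man could decide Stage 1.** This would need a cohort sitting exactly at 3 responses in 23, and the sponsor also weighs the totality of data. Suppose 3% of men fell in the band and every result were read in nM; both figures are assumptions without a source. Stage 1 would then hold 23 × 0.03 = 0.69 such men. At the Table 8 response rates of 10% and 26%, that is 0.07 to 0.18 responders, and fewer if some results are read in ng/dL.

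The reply does not remove the contradiction. One operative criterion states two different limits, and nothing in either document says which applies.

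**Conclusion.** The point holds as an arithmetic error in an eligibility threshold. I07 contradicts itself by about 15% (15.2% to 15.6% over the molar masses tried), and both places that state it carry the same error. The only outside input is the molar mass, and no plausible value changes the conclusion.

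The consequence is limited to mCRPC patients whose result lies between the two figures. For them, eligibility, deviation status and membership of the response evaluable population are not defined until the limits are reconciled. Up to three cohorts of 49 use the criterion: A-1, A-2 if A-1 advances, and possibly C. The number of men affected is probably very small and cannot be derived from the documents. That sites actually differ in reporting unit is a possibility left open by local testing; the documents do not state it. The error does not bias the primary RR, alter the design's operating characteristics or call the mCRPC population into question.

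Which of the two limits is clinically right is for the sponsor to say and is not judged here.

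**What to change.** 1. **Reconcile I07 in the Clinical Trial Summary and in Section 7.2.** The sponsor states which limit is intended and prints its true conversion beside it. If the mass figure is intended, 50 ng/dL pairs with 1.73 nM. If the molar figure is intended, 2.0 nM pairs with 57.7 ng/dL.
2. **Check the screening testosterone values already collected in mCRPC patients,** including any cross-over re-screening, for results between the two figures.
3. **Classify any such patient consistently,** by the reconciled limit, for protocol deviations and for the response evaluable population, before database lock. If no one falls in the band, record that and stop. No additional RR analysis is needed.

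The cost is one number corrected in two places and a query on values already held. The downside is that a very small number of men may be reclassified.

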# For NSCLC patients (I12 to I16):

- I 12. Histologically or cytologically confirmed diagnosis of Stage IIIB/IV or inoperable recurrent NSCLC.
- I 13. At least 1 measurable disease per RECIST 1.1 criteria. Target lesions may be located in a previously irradiated field if there is documented radiographic disease progression in that site
- I 14. One previous anti-PD-1/PD-L1 (nivolumab, pembrolizumab, atezolizumab, durvalumab, avelumab, or REGN2810) containing regimen as the most recent prior therapy to treat Stage IIIB/IV or inoperable recurrent NSCLC. An anti-PD-1/PD-L1 containing regimen is defined as either an anti-PD-1/PD-L1 monotherapy, or an anti-PD-1/PD-L1 agent administered in the same cycle as another systemic therapy.
- I 15. No more than 1 previous chemotherapy regimen to treat Stage IIIB/IV or inoperable recurrent NSCLC.
- I 16. Documented benefit (defined as CR, PR or SD at ≥1 radiographic imaging scan) but subsequent progression per RECIST 1.1 during the PD-1/PD-L1 containing regimen within 4 months prior to initiation of IMP. The site's study team must have reviewed previous tumor assessments (including screening tumor imaging) to determine that radiographic progression has occurred per RECIST 1.1 following initiation of the anti-PD-1/PD-L1 containing regimen.

#### 7.3 EXCLUSION CRITERIA

Patients who have met all the above inclusion criteria listed in Section 7.2 will be screened for the following exclusion criteria:

- E 01. Eastern Cooperative Oncology Group (ECOG) performance status of  $\geq 2$  (Appendix C).
- E 02. Predicted life expectancy <3 months.
- E 03. Prior treatment with an agent (approved or investigational) that blocks CD38 (patients who joined a study with an anti-CD38 but have written confirmation they were on control arm are allowed).
- E 04. For patients with mCRPC, prior treatment with an agent (approved or investigational) that blocks the PD-1/PD-L1 pathway (patients who joined a study with an anti-PD-1/PD-L1 but have written confirmation they were on control arm are allowed).
- E 05. Active brain metastases or leptomeningeal metastases. Patients with asymptomatic central nervous system metastases which have been stable (defined as without evidence of progression by MRI or other imaging modality for at least 28 days prior to initiation of IMP and any neurologic symptoms have returned to baseline) following treatment with surgery or radiation therapy are allowed.
- E 06. Symptomatic or impending cord compression.
- E 07. Prior solid organ or hematologic transplant.
- E 08. Last dose of prior investigational agent within 28 days from initiation of IMP.
- E 09. Treatment-related immune-mediated (or immune-related) AEs from immune-modulatory agents (including but not limited to anti-PD-1/PD-L1 agents, anti-CTLA-4 monoclonal antibodies, and PI3K  $\delta$  inhibitors) that caused permanent discontinuation of the agent, or that were Grade 3 or 4 in severity, or that have not resolved to baseline at least 3 months prior to initiation of IMP. For other agents, treatment-related immune-mediated (or immune-related) AEs that were Grade 2 or above.
- E 10. Prior IV cytotoxic chemotherapy, antineoplastic biological therapy, major surgery, local prostatic intervention within 21 days prior to initiation of IMP; oral cytotoxic chemotherapy, hormonal therapy, tyrosine kinase inhibitor therapy, or completed palliative radiotherapy within 14 days prior to initiation of IMP.
- E 11. Denosumab or bisphosphonate therapy initiation or dose/regimen adjustment within 28 days prior to initiation of IMP. Patients on a stable regimen are eligible and may continue their therapy without change.
- E 12. Comorbidity requiring corticosteroid therapy (>10 mg prednisone/day or equivalent) within 14 days of IMP initiation. Physiologic replacement doses are allowed even if they are >10 mg of prednisone/day or equivalent, as long as they are not being administered for immunosuppressive intent. Inhaled or topical steroids are permitted, provided that they are not for treatment of an autoimmune disorder.

- E 13. Significant cardiac dysfunction, New York Heart Association classification for chronic heart failure III-IV, symptomatic coronary artery disease, major clinically significant electrocardiogram (ECG), significant ventricular arrhythmias; myocardial infarction within 6 months; unstable or poorly controlled angina pectoris.
- E 14. Ongoing AEs (excluding alopecia and fatigue) caused by any prior anti-cancer therapy ≥Grade 2 (NCI-CTCAE version 4.03).
- E 15. Active, known or suspected autoimmune disease that has required systemic treatment in the past 2 years (ie, with use of disease modifying agents, corticosteroids or immunosuppressive drugs), except for replacement therapy (eg, thyroxine, insulin, or physiologic corticosteroid replacement therapy for adrenal or pituitary insufficiency).
- E 16. History of or current interstitial lung disease or pneumonitis that requires oral or IV glucocorticoids to assist with management (radiation pneumonitis in the radiation field is permitted); history of thoracic radiation therapy of >30 Gy within 6 months of the first dose of trial treatment.
- E 17. Receipt of a live-virus vaccination within 28 days of planned treatment start. Seasonal flu vaccines that do not contain live virus are permitted.
- E 18. Known uncontrolled infection with human immunodeficiency virus, known uncontrolled hepatitis B infection, active tuberculosis, or severe infection requiring parenteral antibiotic treatment. To control HBV infection, patients with positive HBsAg should have started anti-HBV therapy before initiation of IMP, and the screening HBV viral load should be <2000 IU/mL (10^4 copies/mL). The anti-HBV therapy should continue throughout the treatment period.
- E 19. Known second malignancy either progressing or requiring active treatment within the last 3 years (except for basal cell carcinoma of the skin, squamous cell carcinoma of the skin, or in situ cervical cancer that has undergone potentially curative therapy).
- E 20. Inadequate organ and bone marrow function at the Screening visit:
  - Absolute neutrophil count (ANC)  $<1500 \text{ u/L} (1 \times 10^9/\text{L}).$
  - Platelets  $<100 \times 10^3$  u/L (after at least 3 days without platelet transfusion).
  - Hemoglobin <9 g/dL or <5.6 mmol/L (without transfusions within 2 weeks of initiation of IMP).
  - Total bilirubin >2 upper limit of normal (ULN).
  - AST and/or ALT > 3 × ULN (or > 5 × ULN for patients with liver metastases).
  - Estimated glomerular filtration rate (eGFR) <30 mL/min/1.73 m^2 (Modified Diet in Renal Disease [MDRD] Formula; Appendix H).

- E 21. Women of reproductive potential and male subjects with female partners of childbearing potential who are not willing to avoid pregnancy 2 weeks before and during the study treatment period and for 6 months following discontinuation of study treatment by using effective contraceptive methods such as:
  - Diaphragm and spermicide PLUS male condom, or
  - Intrauterine device PLUS male condom, or
  - Medical method (such as hormonal contraceptive) PLUS male condom.
  - A woman of productive potential is a woman who: 1) has achieved menarche at some time point, 2) has not undergone a hysterectomy or bilateral oophorectomy or 3) has not been naturally postmenopausal (amenorrhea following cancer therapy does not rule out childbearing potential) for at least 24 consecutive months (ie, has had menses at any time in the preceding 24 consecutive months). The choice of effective method is left to Investigator judgment, in accordance to local regulation. Sterilized or infertile subjects are exempted from the requirement to use of contraception. In order to be considered sterilized or infertile, subjects must have undergone surgical sterilization (vasectomy/bilateral tubectomy, hysterectomy, bilateral ovariectomy) or be a postmenopausal woman defined as 12 months or more with no menses prior to enrollment and 50 years of age. True abstinence is acceptable when this is in line with the preferred and usual lifestyle of the patient. Periodic abstinence (eg, calendar, ovulation, symptothermal, postovulation methods) and withdrawal are not acceptable methods of contraception.
- E 22. Pregnant or breastfeeding woman or woman who intends to become pregnant during the participation in the study.
- E 23. Known intolerance or hypersensitivity to any component of isatuximab and/or REGN2810.
- E 24. History or current evidence of any condition, therapy or laboratory abnormality that might confound the results of the trial, interfere with the subject's participation for the full duration of the trial or is not in the best interest of the subject to participate, in the opinion of the treating Investigator.
- E 25. Patients who will receive REGN2810: prior treatment with idelalisib.
- E 26. Known epidermal growth factor (EGFR) sensitizing mutation, anaplastic lymphoma kinase (ALK) rearrangement, ROS1 rearrangement, or BRAF mutation for patients with non-squamous NSCLC.

Re-screening once is allowed.

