  - Absolute neutrophil count <1500 /uL (1.5 × 10^9/L).
  - Platelets <100 × 10^3 u/L (after at least 3 days without platelet transfusion).
  - Hemoglobin <9 g/dL or <5.6 mmol/L (without transfusions within 2 weeks of initiation of IMP).
  - Total bilirubin >2 upper limit of normal (ULN).
  - Aspartate aminotransferase and/or alanine aminotransferase
     >3 × ULN (or >5 × ULN for patients with liver metastases).
  - Estimated glomerular filtration rate (eGFR) <30 mL/min/1.73 m^2 (Modified Diet in Renal Disease Formula).
- E 21. Women of reproductive potential and male subjects with female partners of childbearing potential who are not willing to avoid pregnancy 2 weeks before and during the study treatment period and for 6 months following discontinuation of study treatment by using effective contraceptive methods such as:
  - Diaphragm and spermicide PLUS male condom, or
  - Intrauterine device PLUS male condom, or
  - Medical method (such as hormonal contraceptive) PLUS male condom.
  - A woman of productive potential is a woman who: 1) has achieved menarche at some time point, 2) has not undergone a hysterectomy or bilateral oophorectomy or 3) has not been naturally postmenopausal (amenorrhea following cancer therapy does not rule out childbearing potential) for at least 24 consecutive months (ie, has had menses at any time in the preceding 24 consecutive months). The choice of effective method is left to Investigator judgment, in accordance to local regulation. Sterilized or infertile subjects are exempted from the requirement to use of contraception. In order to be considered sterilized or infertile, subjects must have undergone surgical sterilization (vasectomy/bilateral tubectomy, hysterectomy, bilateral ovariectomy) or be a postmenopausal woman defined as 12 months or more with no menses prior to enrollment and 50 years of age. True abstinence is acceptable when this is in line with the preferred and usual lifestyle of the patient. Periodic abstinence (eg. calendar, ovulation, symptothermal, postovulation methods) and withdrawal are not acceptable methods of contraception.
- E 22. Pregnant or breastfeeding woman or woman who intends to become pregnant during the participation in the study.
- E 23. Known intolerance or hypersensitivity to any component of isatuximab and/or REGN2810.

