## 13.3.7 Response evaluable population

The response evaluable population will include all patients in the all-treated population who fulfill all eligibility criteria with an evaluable baseline assessment and at least one evaluable post-baseline response assessment during the treatment period.

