12.2 Baseline evaluation 12.3.1 Cycle 1 (Day 1, Day 8 and Day 15)		
12.3.2 Subsequent cycles (Day 1) 12.4 End of treatment		
12.5.1 Safety follow-up period		

1.3 Study flowchart for Phase 1, Phase

2 Cohorts A-1, A-2, B and cross-over part

1.4 Study flowchart for Cohort C and Cohort D

	To allow semi-quantitative urinalysis	Allow semi-quantitative urinalysis if semi-quantitative method used at site level can provide an absolute numeric value of the parameters.

Section # and Name	Description of Change	Brief Rationale
Throughout	Miscellaneous clarifications,	Includes but not limited to:
	correction of inconsistencies	Correct typo in E14 and E20
	and typographic errors	Correct indicative clocks and clarify sampling timing in PK flow chart
		Biomarker exploratory endpoints stated in the Clinical Trial Summary is now also inserted under Section 9.6.3 Exploratory endpoints
		Remove biomarker sample preservation methods (keep details in laboratory manual)
		Correct units and typos of absolute neutrophil count under E20
		Clarify isatuximab monotherapy dose is to be determined depending on the recommended Phase 2 dose
		Clarify inform consent form can be signed more than 28 days prior to enrollment/randomization at define screening period time frame, and redefine "pretreatment AEs" as AEs during "pretreatment period" instead of "screening period"
		Introduce INN (cemiplimab) when REGN2810 wa first mentioned and in Introduction
		Remind study sites must retain disease assessment images as Sponsor may decide to collect images in the future for possible Independent Central Review
		Inconsistencies in visit schedule
		AESI specified in Section 6.6.4 was not mentione in Section 10.5.5

ANSM= Agence Nationale de Sécurité du Médicament et des Produits de Santé; DCR=disease control rate; DoR=duration of response; EOT=end of treatment; IMP=investigational medicinal product; mCRPC=metastatic castration-resistant prostate cancer; MHRA= Medicines and Healthcare Products Regulatory Authority; PD=disease progression; PFS=progression-free survival

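### Protocol section 7.3 E20 pairs a neutrophil limit of 1500 with 1 × 10^9/L, which is not the same threshold and disagrees with the 1.5 × 10^9/L in the Clinical Trial Summary

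*Protocol*

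**What the plan says.** E20 excludes patients with inadequate organ or marrow function at screening. It is printed twice in the current protocol.

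- **Clinical Trial Summary, exclusion criteria, E20:** "Absolute neutrophil count <1500 /uL (1.5 × 10 9 /L", that is, 1500 per microlitre with 1.5 × 10^9/L in brackets.
- **Section 7.3, E20:** the line opens "Absolute neutrophil count (ANC" and continues, in formula notation, "<1500 \text{ u/L} (1 \times 10^9/\text{L", that is, 1500 with 1 × 10^9/L in brackets.

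Section 12.2 (baseline evaluation) requires every inclusion criterion and no exclusion criterion to be met and refers the reader to Section 7, so section 7.3 is the operative list. Section 6.4 requires Cohort A-2 patients who cross over to meet the eligibility criteria again, apart from exclusions 3 and 8, so E20 is applied a second time to them.

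Eligibility also enters the analysis. Under section 13.3.7 the response evaluable population consists of treated patients "who fulfill all eligibility criteria with an evaluable baseline assessment" and at least one evaluable assessment after baseline. SAP section 2.3.7 has the same requirement.

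As context only, the Amendment 3 entry in Appendix J lists the item "Correct units and typos of absolute neutrophil count under E20". That log describes changes to superseded text and is not itself evidence of an error. The point here rests on the two current E20 lines.

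**The concern.** One line of the operative eligibility list carries two limits that cannot both be the limit. E20 is a safety entry criterion, and section 9.1.1 counts certain neutropenia events as dose-limiting toxicities, so the baseline neutrophil requirement ought to be unambiguous.

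The bracketed figure would not obviously strike a reader as a slip. The flowchart notes and section 12.2 state neutrophil monitoring limits in 10^9/L, one of them at 1.0 × 10^9/L, and Table 2 in section 6.6.3 uses 1000/mm³ as a level for resuming treatment. Haematology is done at local laboratories across about 15 sites. The SAP (section 2.1.4.5 and Appendix A, Table 6) works in international units, with neutrophils in 10^9/L. A site whose laboratory reports in that unit could reasonably look to the bracket.

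Three things depend on having one threshold: who may be enrolled or cross over, which enrolled patients are protocol deviators (section 13.2.2), and who belongs to the response evaluable population.

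**Working it through.** **Inputs**

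- Count printed in both places: 1500 (Clinical Trial Summary E20; section 7.3 E20).
- Bracketed SI figure, Clinical Trial Summary: 1.5 × 10^9/L.
- Bracketed SI figure, section 7.3: 1 × 10^9/L.
- Conversion: 1 L = 10^6 microlitres.

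**Step 1: reproduce the summary's pair.** 1500 per microlitre × 10^6 microlitres/L = 1.5 × 10^9/L. This matches what is printed.

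**Step 2: try the same for section 7.3.** The count is again 1500, so the SI equivalent is again 1.5 × 10^9/L. The printed figure is 1 × 10^9/L, so it is not reproduced.

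**Step 3: convert the section 7.3 bracket back.** 1 × 10^9/L ÷ 10^6 microlitres/L = 1000 per microlitre.

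**Step 4: size of the gap.** 1500 − 1000 = 500 per microlitre, and 500 / 1500 = one third of the printed count.

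**Step 5: what each figure does to a patient in the gap**

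| Screening count (10^9/L) | Clinical Trial Summary (1500/µL = 1.5) | Section 7.3, count of 1500 | Section 7.3, bracket of 1 |
|---|---|---|---|
| below 1.0 | excluded | excluded | excluded |
| 1.0 to under 1.5 | excluded | excluded | not excluded |
| 1.5 or above | not excluded | not excluded | not excluded |

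Only the middle row is in dispute.

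**Step 6: trace the analysis consequence.** The all-treated population (Protocol 13.3.1, SAP 2.3.1) is defined by consent and at least one dose, and it is primary for efficacy and safety; eligibility plays no part. Section 13.4.4.1 uses the response evaluable population for a secondary analysis of response rate, and SAP section 2.4.5 repeats efficacy analyses in it as an addition. The stage sizes and response counts in section 13.1 do not involve E20.

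**The case against.** The best case on the other side has four parts.

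**The weight of the text points one way.** The count of 1500 is the same in both places and the summary's pair is self-consistent, so three printed figures agree and one bracket stands apart. A careful site would notice. E24 also lets the investigator exclude a patient for a laboratory abnormality on other grounds. This stands as a reason to expect limited practical effect, but it does not remove the contradiction: no other current text says which figure governs.

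**Nothing shows that a site used the bracket.** A reader might infer that sites working in SI units did enrol to a lower threshold, or that every screened patient between 1.0 and 1.5 × 10^9/L was affected. The documents support neither. They do not record which figure was used, and the haemoglobin limit, which is given in two units joined by an explicit alternative, does not establish that a bracketed neutrophil figure was meant for site use. What the text supports is that such a patient could be judged either way.

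**The decimal may have been lost in reading the PDF.** The section 7.3 line is set as a formula and the summary line is not. This cannot be excluded from the text alone. Against it, other decimals in the same E20 list of section 7.3 survive (5.6 mmol/L for haemoglobin, 1.73 m² for eGFR). The source page should be checked first.

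**The printed unit is not separate evidence.** Section 7.3 prints u/L for neutrophils, which taken literally gives neither threshold. The platelet limit carries the same unit in both versions of E20, so this looks like a general rendering of the unit and adds nothing on the threshold. That objection is accepted.

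**Conclusion.** The inconsistency is real in the current text. Section 7.3 E20 states two neutrophil thresholds, 500 per microlitre (one third) apart, and its SI figure disagrees with the Clinical Trial Summary. The patients for whom this matters are those with a screening count from 1.0 to just under 1.5 × 10^9/L; their number is not given and cannot be derived.

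The consequence is modest. It reaches eligibility at entry and at cross-over, the classification of protocol deviations, and membership of the population behind a secondary response-rate analysis. A reader might infer that the primary response-rate result or the go/no-go rules are compromised. They are not, because both rest on all treated patients and on design figures that do not depend on E20.

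The conclusion assumes that the source page prints 1 × 10^9/L. If the page shows 1.5, the point falls away. No view is taken on which threshold is clinically appropriate.

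**What to change.** 1. Check the section 7.3 E20 line on the source PDF page for a lost decimal.
2. If the mismatch is there, the sponsor should reconcile section 7.3 with the Clinical Trial Summary so that both carry one neutrophil threshold with a consistent unit conversion.
3. Notify sites of the reconciled wording. Before the response evaluable population is fixed, check any enrolled or crossed-over patient whose screening count lies from 1.0 to under 1.5 × 10^9/L, so that deviation calls and population membership follow the same figure.

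The cost is one line in the protocol and a site memo. The listing in step 3 uses screening haematology that is already collected.
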